### 5.1 Subject Inclusion Criteria

Subjects must meet all of the inclusion criteria to be enrolled in this study.

1. Clinician suspected LRTI based on the presence of at least two qualifying symptoms OR one qualifying symptom and at least one qualifying vital sign.

 LRTI will include acute bronchitis, tracheitis, tracheobronchitis, asthma exacerbation, and acute exacerbation of COPD but does not include known pneumonia.

 New cough, worsening of chronic cough, new sputum production, increased volume or purulence of chronic sputum production, chest pain, and difficulty breathing

 Fever (Provider or patient-measured temperature  $\geq 37.8^{\circ}\text{C}$  ( $100.0^{\circ}\text{F}$ ) or patient-reported feverishness), tachycardia of  $\geq 90$  beats/minute, tachypnea of  $>20$  breaths/minute

2. Males and females age  $\geq 18$  years old.
3. Presentation  $\geq 24$  hours and  $\leq 28$  days after the onset of at least one qualifying symptom related to the acute episode of illness.
4. Ability to understand study procedures and willing and able to comply with all required procedures and visits for the entire length of study.
5. Provide written informed consent before initiation of any study procedures.

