10. Using the ATP-5 analysis population, forest plots of 95% confidence intervals for the difference in proportions of subjects with each solicited event (a component of DOOR) collected through Visit 3, for each severity threshold (mild or greater, moderate or greater, or severe) will be generated. Tests for differences in proportions between treatment arms will be given by Fisher's exact tests.
11. Using the ATP-5 analysis population, a forest plot of 95% confidence intervals for the difference in proportions of subjects with one or more visits to an ED, one or more visits to an outpatient clinic, or one or more visits to an urgent care center or one or more hospitalizations for persistent or worsening LRTI at any time after randomization (a component of clinical improvement and DOOR) will be generated. Tests for differences in proportions between treatment arms will be given by Fisher's exact tests.
12. Using the ATP-5 analysis population, for each qualifying vital sign (temperature, pulse, respiratory rate, or pulse oximetry) and symptom (cough, sputum production, chest pain, or difficulty breathing), improvement in the sign or symptom at Visit 3 compared to baseline in subjects with the symptom or vital sign abnormality at baseline (a component of clinical improvement and DOOR) will be analyzed. A forest plot of 95% confidence intervals for the difference in proportions of subjects with improvement in the symptom or sign will be generated. Tests for differences in proportions between treatment arms will be given by Fisher's exact tests.
13. Using the ATP-5 analysis population, for each qualifying symptom (cough, sputum production, chest pain, or difficulty breathing), deterioration in the symptom at Visit 3 compared to baseline (a component of clinical improvement and DOOR) will be analyzed in subjects having the symptom at baseline. A forest plot of 95% confidence intervals for the difference in proportions of subjects with deterioration in the symptom will be generated. Tests for differences in proportions between treatment arms will be given by Fisher's exact tests.

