3.3.2. Clinical Improvement at D5V

Clinical improvement at D5V is defined as fulfillment of **all** the following criteria.

1. Improvement in at least two symptoms present at enrollment (i.e., cough, sputum production, chest pain, or difficulty breathing) *or* one symptom and at least one vital sign abnormality present at enrollment. For symptoms, at least a one-step improvement (e.g., improvement from moderate to mild cough) will be considered a clinical improvement (Table 1). For vital sign abnormalities,

normalization of the presenting abnormal vital sign will be considered a clinical improvement. Qualifying vital signs and their normal values will include the following:

- temperature (<37.8°C or 100.0°F),
 - pulse (<90 bpm),
 - respiratory rate (≤20 breaths per minute),
2. Absence of deterioration in any qualifying symptom (i.e., cough, sputum production, chest pain, or difficulty breathing); or new vital sign abnormality not present at enrollment. For symptoms, at least a one-step deterioration (e.g. worsening from mild to moderate cough) will be considered clinical deterioration.
 3. Absence of fever in the day preceding or at the D5V (fever is defined as ≥37.8 °C or 100.0 °F, measured anywhere on the body).
 4. No medically attended visit to an ambulatory medical facility (e.g., ED, outpatient clinic, urgent care center) or hospitalization for persistent or worsening LRTI at any time after randomization (persistent or worsening LRTI is defined as receipt of a non-study antibiotic [parenteral or oral] treatment for LRTI or its complication). **Note:** receipt of a non-study antibiotic after study day 5 will not be regarded as satisfying this definition if it is related to a new non-respiratory process that is unrelated to the prior diagnosis of LRTI

Table 1: LRTI-Related Symptoms to Define Clinical Improvement Endpoint

	Mild	Moderate	Severe
Cough*	Occasional coughing (less than hourly)	Frequent coughing (1 or more times an hour and interferes with activity or sleep)	Almost constant coughing (never free of cough or need to cough, makes activity or sleep nearly impossible)
Sputum production*	Noticeable as a problem but does not interfere with activity	Causes a great deal of inconvenience	An almost constant problem
Chest pain	Noticeable only when coughing	Noticeable during deep breaths and when coughing	Almost constant, present even when resting, without cough

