8.2.10. Analysis of Medically Attended Events at D5V Using ATP-5 Analysis Populations

A forest plot of 95% CIs for the risk difference of one or more visits to an ED, one or more visits to an outpatient clinic, or one or more visits to an urgent care center or one or more hospitalizations for persistent or worsening LRTI at any time after randomization will be produced for D5V using ATP-5 analysis population in [Figure 8](#) and results will also be presented in [Table 43](#) to include a p-value from Fisher's exact test. Since Fisher's test cannot be inverted, there is no corresponding CI. Therefore, the Miettinen–Nurminen method will be used to compute all 95% CIs for risk differences. Note that the CI results might not be consistent with the p-value from Fisher's exact test. [Listing 19](#) contains all medically attended visits while [Listing 20](#) provides a listing of all hospitalizations.

8.2.11. Improvement in Qualifying Symptoms or Vital Signs at D5V Using ATP-5 Analysis Population

The proportions of subjects exhibiting improvement in one qualifying symptom (cough, sputum production, chest pain, or difficulty breathing) or vital sign (temperature, pulse, respiratory rate, or pulse oximetry) at Visit 3 compared to baseline will be computed for placebo versus azithromycin along with associated 95% CIs using ATP-5 population. A forest plot of 95% CIs for the difference in proportions of subjects with improvement in any symptom or sign, any symptom, any sign, at least two symptoms or signs, and each individual symptom or sign will be provided in [Figure 10](#). Results will also be reported in [Table 41](#), and tests for differences in proportions between treatment arms will be given by Fisher's exact tests. Since Fisher's test cannot be inverted, there is no corresponding CI. Therefore, the Miettinen–Nurminen method will be used to compute the 95% CIs for risk differences. Note that the CI results might not be consistent with the p-value from Fisher's exact test.

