n = Number of subjects with at-least one step deterioration (worsening from mild to moderate for example) in any qualifying symptom regardless whether the symptom was present at enrollment or not.
^a95% CI for proportions calculated using the Wilson method.
^b95% CI for the difference in proportions, placebo relative to azithromycin, calculated using the Miettinen–Nurminen method.
^cP-values obtained by Fisher’s Exact Test.

Table with similar format:

Table 40: Deterioration in LRTI Symptoms at D11V - ATP-11 Analysis Population

[Implementation Note: Update the footnote to use ATP-11.]

Table 41: Improvement in Symptom or Vital Sign - ATP-5 Analysis Population

Symptom	Azithromycin				Placebo				Difference (95% CI) ^b	P-Value ^c
	N	n	%	95% CI ^a	N	n	%	95% CI ^a		
Any Symptom or Sign	x	x	x	(x.x, x.x)	x	x	x	(x.x, x.x)	xx (x.x, x.x)	x.xxx
Any Symptom	x	x	x	(x.x, x.x)	x	x	x	(x.x, x.x)	xx (x.x, x.x)	x.xxx
Any Sign	x	x	x	(x.x, x.x)	x	x	x	(x.x, x.x)	xx (x.x, x.x)	x.xxx
At Least 2 Symptoms or Signs	x	x	x	(x.x, x.x)	x	x	x	(x.x, x.x)	xx (x.x, x.x)	x.xxx
Cough	x	x	x	(x.x, x.x)	x	x	x	(x.x, x.x)	xx (x.x, x.x)	x.xxx
Sputum Production	x	x	x	(x.x, x.x)	x	x	x	(x.x, x.x)	xx (x.x, x.x)	x.xxx
Chest Pain	x	x	x	(x.x, x.x)	x	x	x	(x.x, x.x)	xx (x.x, x.x)	x.xxx
Difficulty Breathing	x	x	x	(x.x, x.x)	x	x	x	(x.x, x.x)	xx (x.x, x.x)	x.xxx
Temperature	x	x	x	(x.x, x.x)	x	x	x	(x.x, x.x)	xx (x.x, x.x)	x.xxx
Pulse	x	x	x	(x.x, x.x)	x	x	x	(x.x, x.x)	xx (x.x, x.x)	x.xxx
Respiratory Rate	x	x	x	(x.x, x.x)	x	x	x	(x.x, x.x)	xx (x.x, x.x)	x.xxx

N = Number of subjects in the ATP-5 analysis population and the respective treatment group with the symptom or vital sign abnormality present at baseline.

n = Number of subjects with the vital sign abnormality at baseline whose symptom or vital sign improved.

^a95% CI for proportions calculated using the Wilson method.

^b95% CI for the difference in proportions, placebo relative to azithromycin, calculated using the Miettinen–Nurminen method.

^cP-values obtained by Fisher's Exact Test.

Table 42: New Occurrence of Vital Sign Abnormality or Presence of Fever at D5V - ATP-5 Analysis Population

Symptom	Azithromycin				Placebo				Difference (95% CI) ^b	P-Value ^d
	N	n	%	95% CI ^a	N	n	%	95% CI ^a		
Any Vital Sign	x	x	x	(x.x, x.x)	x	x	x	(x.x, x.x)	xx (x.x, x.x)	x.xxx
Temperature	x	x	x	(x.x, x.x)	x	x	x	(x.x, x.x)	xx (x.x, x.x)	x.xxx
Pulse	x	x	x	(x.x, x.x)	x	x	x	(x.x, x.x)	xx (x.x, x.x)	x.xxx

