Respiratory Rate	x	x	x	(x.x, x.x)	x	x	x	(x.x, x.x)	xx (x.x, x.x)	x.xxx
Fever in the 24 hours preceding or at D5V	x	x	x	(x.x, x.x)	x	x	x	(x.x, x.x)	xx (x.x, x.x)	x.xxx

N = Number of subjects in the ATP-5 analysis population and the respective treatment group without the vital sign abnormality at baseline. For fever, N was defined as the total number of subjects with non-missing fever at D5V.
n = Number of subjects with normal vital sign at baseline, but who developed abnormal vital sign at D5V. For fever, n was defined as number of subjects with fever in the 24 hours preceding or at D5V as defined in Section 6.5.1.3.
^a95% CI for proportions calculated using the Wilson method.
^b95% CI for the difference in proportions, placebo relative to azithromycin, calculated using the Miettinen–Nurminen method.
^cP-values obtained by Fisher’s Exact Test.

Table 43: Any Medically Attended Visit for Persistent or Worsening LRTI - ATP-5 Analysis Population

Symptom	Azithromycin (N=X)			Placebo (N=X)			Difference (95% CI) ^b	P-Value ^c
	n	%	95% CI ^a	n	%	95% CI ^a		
Any MAV	x	x	(x.x, x.x)	x	x	(x.x, x.x)	xx (x.x, x.x)	x.xxx
One or more visits to ED	x	x	(x.x, x.x)	x	x	(x.x, x.x)	xx (x.x, x.x)	x.xxx
One or more visits to an outpatient clinic	x	x	(x.x, x.x)	x	x	(x.x, x.x)	xx (x.x, x.x)	x.xxx
One or more visits to an urgent care center	x	x	(x.x, x.x)	x	x	(x.x, x.x)	xx (x.x, x.x)	x.xxx
One or more hospitalizations	x	x	(x.x, x.x)	x	x	(x.x, x.x)	xx (x.x, x.x)	x.xxx

N = Number of subjects in the ATP-5 analysis population and the respective treatment group.
^a95% CI for proportions calculated using the Wilson method.
^b95% CI for the difference in proportions, placebo relative to azithromycin, calculated using the Miettinen–Nurminen method
^cP-values obtained by Fisher’s Exact Test.

Table with similar format:

Table 44: Any Medically Attended Visit for Persistent or Worsening LRTI - ATP-11 Analysis Population

[Implementation Note: Update the footnote to use ATP-11.]

Table 45: Analysis of Fever in the 24 Hours Preceding or at D11V

Analysis Population	Statistic	Value
ATP-11	Subjects with fever in the 24 hours preceding or at D11V – n (%)	
	Azithromycin (N=X)	x (xx)
	Placebo (N=X)	x (xx)
	Difference in Proportions, placebo relative to azithromycin (95% CI) ^a	xx.x (xx, xx)
	P-value ^b	x.xxx

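### SAP Table 41: the numerator footnote requires a baseline vital sign abnormality that the denominator and the protocol do not, so the symptom and mixed rows would be understated if programmed as written

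*SAP*

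**What the plan says.** Table 41 (SAP Appendix 1, under 14.2 Efficacy Data) is the shell for the analysis in SAP Section 8.2.11. It has four composite rows (any symptom or sign, any symptom, any sign, and "At Least 2 Symptoms or Signs"), then one row each for cough, sputum production, chest pain, difficulty breathing, temperature, pulse and respiratory rate. Two footnotes define the counts for every row:

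- The denominator footnote takes ATP-5 subjects in the arm "with the symptom or vital sign abnormality present at baseline", so either a symptom or a sign is enough to be counted.
- The numerator footnote is narrower and mentions only the sign when it describes baseline: "n = Number of subjects with the vital sign abnormality at baseline whose symptom or vital sign improved".

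The text that governs the table has no such limit on the numerator. Protocol Section 11.4.2 item 12 analyses "improvement in the sign or symptom at Visit 3 compared to baseline in subjects with the symptom or vital sign abnormality at baseline". SAP Section 8.2.11 opens with "The proportions of subjects exhibiting improvement in one qualifying symptom (cough, sputum production, chest pain, or difficulty breathing) or vital sign" and does not confine symptom improvement to subjects with an abnormal sign. The corresponding Day 11 shell, Table 35, defines n as subjects with improvement, with no further condition.

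Protocol Section 5.1 lets a subject enter "based on the presence of at least two qualifying symptoms", with a vital sign needed only when there is a single symptom.

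**The concern.** In a symptom row the two footnotes describe different sets of people. Someone with cough and sputum and normal vital signs at enrollment counts in N for both rows. However much that person improves, the n footnote shuts them out. The percentage is then not a proportion of the people it is printed against.

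The at-least-two row is the display for secondary outcome 11 (improvement in at least two presenting signs or symptoms at Day 5). The percentages, Wilson intervals, Miettinen–Nurminen differences and Fisher p-values in the affected rows would all carry the error, as would the same differences in the forest plot (Figure 10). If the programmer instead does the sensible thing, the numbers are right but the printed footnote misdescribes them.

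**Working it through.** The plan states no figure to reproduce, since Table 41 is an empty shell. The check is a comparison by row, followed by an illustration on stated assumptions.

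**Step 1. Which rows are affected.**

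| Rows | In N | Allowed into n by the footnote | Match? |
|---|---|---|---|
| Temperature, pulse, respiratory rate, any sign | Subjects with that abnormal sign (or any abnormal sign) | The same subjects | Yes |
| Cough, sputum, chest pain, difficulty breathing, any symptom | Subjects with that symptom (or any symptom) | Only those who also had an abnormal vital sign | No |
| Any symptom or sign, at least two | Subjects with symptoms, signs or both | Only those with an abnormal vital sign | No |

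**Step 2. Direction.** Literal n equals true n minus the improvers whose baseline vital signs were normal. The loss is zero only if there are no such improvers. Entry on two symptoms alone makes them possible by design.

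**Step 3. Size, as an illustration.** Let r be the true improvement rate in a symptom row and v the share of that row's N with an abnormal vital sign at baseline. Assume improvement is independent of v. The documents give neither r nor v. Then

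printed rate = v × r; printed difference = v × true difference, if v is equal in both arms.

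| v (assumed) | r = 60% prints as | A true −10 points prints as |
|---|---|---|
| 0.2 | 12% | −2 |
| 0.4 | 24% | −4 |
| 0.6 | 36% | −6 |
| 0.8 | 48% | −8 |
| 1.0 | 60% | −10 |

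Shrinkage is not the only possible distortion. With r = 60% in both arms but v = 0.40 on azithromycin and 0.45 on placebo, the printed rates are 24% and 27%. That is a difference of 3 points where none exists.

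**Step 4. A consistency check on counts.** Clinical improvement at Day 5 (SAP Sections 3.3.2 and 6.5.1.1) requires two improved symptoms, or one improved symptom and one normalised sign. Every ATP-5 subject counted as improved in Table 22 should therefore also count in the at-least-two row of Table 41. At the planning values in SAP Section 5, that is 560 × 0.576 = 322.6, or about 323 subjects. The literal footnote caps the row's n at 560 × v, with v now the share of all ATP-5 subjects:

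- v = 0.30 gives at most 168, below 323, which cannot be right.
- v = 0.60 gives at most 336, so 323/336 = 96% of those subjects would have to be improvers.

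At these planning values, any v below 57.6% would force the row's n under the Table 22 count.

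**The case against.** The strongest reply is that this is a slip in a mock-up. Protocol Section 11.4.2 item 12 states the analysis correctly, SAP Section 8.2.11 has no vital sign restriction, and Table 35 is worded without one. In a cough row the phrase about the vital sign abnormality refers to nothing, so a couple of words were probably dropped. That is very likely the explanation, and it is why the understatement is conditional on the footnote being followed. It does not remove the point. Section 8.2.11 gives no row-level numerator, so the footnote is the SAP's only operational definition of n for this table.

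A second reply is that Table 22 and Table 41 would not agree even with a correct footnote, because Table 22's rates are adjusted to study day 5 and refer to a four-part composite. That holds for the percentages. It does not touch the count comparison above, since Table 22 also prints the number of improved subjects.

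A reader might also infer three stronger things, none of which the documents support:

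- **That criterion 1 of the primary endpoint is understated.** Criterion 1 is derived from subject-level forms under SAP Section 6.5.1.1, not from Table 41. Nor is the at-least-two row the same thing: two normalised signs with no symptom improvement would count there but would not meet criterion 1.
- **That the trial is tilted towards non-inferiority.** SAP Section 8.1.1 rests that conclusion on the primary ITT analysis alone. Table 41 carries no margin, and Step 3 shows the distortion need not favour placebo.
- **That Table 42 has the same error.** Its numerator ("n = Number of subjects with normal vital sign at baseline, but who developed abnormal vital sign at D5V") agrees with its denominator, and row by row both match Protocol Section 11.4.2 item 14. What is missing is only an explicit N for its any-vital-sign row. A subject with one abnormal sign at baseline who develops another has a "new vital sign abnormality not present at enrollment", and it is unclear whether that subject belongs in the composite row. That is a clarification, not an error.

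**Conclusion.** The Table 41 footnotes conflict with each other, and the n footnote conflicts with the protocol. Programmed as written, the four symptom rows, the any-symptom row and the two mixed rows would be understated whenever some improvers had normal baseline vital signs, and their between-arm differences would be shrunk or otherwise distorted. The individual sign rows, the any-sign row and the primary analysis do not change.

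The documents do not allow the amount to be computed. The illustrative figures depend on assumed values of v and r and on independence between them; at v = 1 there is no understatement. The point deserves correction because a pre-specified secondary outcome is reported from this table, but it is a table-shell correction and has no bearing on the non-inferiority conclusion.

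**What to change.** Replace the Table 41 n footnote with row-specific definitions, and state N for the composite rows:

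- **Single symptom or sign rows:** n is the number of subjects in that row's N in whom that same symptom improved by at least one step, or that same vital sign normalised, at D5V.
- **The three any-type rows:** N is subjects with at least one of the row's listed items at baseline; n is those in whom at least one item present at baseline improved.
- **At-least-two row:** N is subjects with at least two of the listed items at baseline; n is those in whom at least two items present at baseline improved.

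The words tying n to the same symptom or sign matter. A looser footnote counting any improved symptom or normalised sign would let a normalised pulse count in the cough row, and a single improvement count in the at-least-two row.

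Optionally, add one sentence to Table 42 giving the N of its any-vital-sign row.

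The cost is a few lines in one table shell, plus the optional sentence in a second. No new data, analysis method or protocol change is needed.

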14.3 Safety Data

14.3.1 Displays of Adverse Events

14.3.1.1 Solicited Adverse Events

Table 65: Number and Percentage of Subjects Experiencing Solicited Events with 95% CIs by Symptom and Treatment Group - Safety Population

Symptom	Azithromycin (N=X)			Placebo (N=X)		
	n	%	95% CI ^a	n	%	95% CI ^a
Any Symptom	x	xx	x, x	x	xx	x, x
Abdominal pain						
Vomiting						
Diarrhea						
Allergic Reaction						
Candidiasis						

N = Number of subjects in the Safety Population in the respective treatment group who have solicited data reported. Severity of the maximum severity reported post dosing for each subject.
^a95% CI for proportions calculated using the Wilson method.

Table 66: Number and Percentage of Subjects Experiencing Solicited Events with 95% CIs by Symptom, Maximum Severity, and Treatment Group - Safety Population

Symptom	Severity	Azithromycin (N=X)			Placebo (N=X)		
		n	%	95% CI ^a	n	%	95% CI ^a
Any Symptom	None	x	xx	x, x	x	xx	x, x
	Mild						
	Moderate						
	Severe						
Abdominal pain	None						
	Mild						
	Moderate						
	Severe						
Vomiting	None						
	Mild						
	Moderate						
	Severe						
Diarrhea	None						
	Mild						
	Moderate						
	Severe						
Allergic Reaction	None						
	Mild						
	Moderate						
	Severe						
Candidiasis	None						
	Mild						
	Moderate						
	Severe						

N = Number of subjects in the Safety Population in the respective treatment group who have solicited data reported. Severity of the maximum severity reported post dosing for each subject.

^a95% CI for proportions calculated using the Wilson method.

Table 67: Number and Percentage of Subjects Experiencing Solicited Events by Symptom, Severity, and Day Post Dosing - Azithromycin Group, Safety Population

		Azithromycin											
		Day 1 (N = X)	Day 2 (N = X)	Day 3 (N = X)	Day 4 (N = X)	Day 5 (N = X)	Day 6 (N = X)	Day 7 (N = X)	Day 8 (N = X)	Day 9 (N = X)	Day 10 (N = X)	Day 11 (N = X)	Any Post Dose (N = X)
Symptom	Severity	n (%)	n (%)	n (%)	n (%)	n (%)	n (%)	n (%)	n (%)	n (%)	n (%)	n (%)	n (%)
Any Symptom	None	x (xx)	x (xx)	x (xx)	x (xx)	x (xx)	x (xx)	x (xx)	x (xx)	x (xx)	x (xx)	x (xx)	x (xx)
	Mild												
	Moderate												
	Severe												
	Not Reported												
Abdominal Pain	None	x (xx)	x (xx)	x (xx)	x (xx)	x (xx)	x (xx)	x (xx)	x (xx)	x (xx)	x (xx)	x (xx)	x (xx)
	Mild												
	Moderate												
	Severe												
	Not Reported												
Vomiting	None												
	Mild												
	Moderate												
	Severe												
	Not Reported												
Diarrhea	None												
	Mild												
	Moderate												
	Severe												
	Not Reported												

Table 67: Number and Percentage of Subjects Experiencing Solicited Events by Symptom, Severity, and Day Post Dosing - Azithromycin Group, Safety Population (Continued)

		Azithromycin											
		Day 1 (N = X)	Day 2 (N = X)	Day 3 (N = X)	Day 4 (N = X)	Day 5 (N = X)	Day 6 (N = X)	Day 7 (N = X)	Day 8 (N = X)	Day 9 (N = X)	Day 10 (N = X)	Day 11 (N = X)	Any Post Dose (N = X)
Symptom	Severity	n (%)	n (%)	n (%)	n (%)	n (%)	n (%)	n (%)	n (%)	n (%)	n (%)	n (%)	n (%)
Allergic Reaction	None	x (xx)	x (xx)	x (xx)	x (xx)	x (xx)	x (xx)	x (xx)	x (xx)	x (xx)	x (xx)	x (xx)	x (xx)
	Mild												
	Moderate												
	Severe												
	Not Reported												
Candidiasis	None												
	Mild												
	Moderate												
	Severe												
	Not Reported												

N = Number of subjects in the Safety Population in the respective treatment group who have solicited data reported on the corresponding day. Severity is the maximum severity reported post dosing for each subject for each day.

Table 68: Number and Percentage of Subjects Experiencing Solicited Events by Symptom, Severity, and Day Post Dosing - Placebo Group, Safety Population

		Placebo											
		Day 1 (N = X)	Day 2 (N = X)	Day 3 (N = X)	Day 4 (N = X)	Day 5 (N = X)	Day 6 (N = X)	Day 7 (N = X)	Day 8 (N = X)	Day 9 (N = X)	Day 10 (N = X)	Day 11 (N = X)	Any Post Dose (N = X)
Symptom	Severity	n (%)	n (%)	n (%)	n (%)	n (%)	n (%)	n (%)	n (%)	n (%)	n (%)	n (%)	n (%)
Any Symptom	None	x (xx)	x (xx)	x (xx)	x (xx)	x (xx)	x (xx)	x (xx)	x (xx)	x (xx)	x (xx)	x (xx)	x (xx)
	Mild												
	Moderate												
	Severe												
	Not Reported												
Abdominal Pain	None	x (xx)	x (xx)	x (xx)	x (xx)	x (xx)	x (xx)	x (xx)	x (xx)	x (xx)	x (xx)	x (xx)	x (xx)
	Mild												
	Moderate												
	Severe												
	Not Reported												
Vomiting	None												
	Mild												
	Moderate												
	Severe												
	Not Reported												
Diarrhea	None												
	Mild												
	Moderate												
	Severe												
	Not Reported												

Table 68: Number and Percentage of Subjects Experiencing Solicited Events by Symptom, Severity, and Day Post Dosing - Placebo Group, Safety Population (Continued)

		Placebo											
		Day 1 (N = X)	Day 2 (N = X)	Day 3 (N = X)	Day 4 (N = X)	Day 5 (N = X)	Day 6 (N = X)	Day 7 (N = X)	Day 8 (N = X)	Day 9 (N = X)	Day 10 (N = X)	Day 11 (N = X)	Any Post Dose (N = X)
Symptom	Severity	n (%)	n (%)	n (%)	n (%)	n (%)	n (%)	n (%)	n (%)	n (%)	n (%)	n (%)	n (%)
Allergic Reaction	None	x (xx)	x (xx)	x (xx)	x (xx)	x (xx)	x (xx)	x (xx)	x (xx)	x (xx)	x (xx)	x (xx)	x (xx)
	Mild												
	Moderate												
	Severe												
	Not Reported												
Candidiasis	None												
	Mild												
	Moderate												
	Severe												
	Not Reported												

N = Number of subjects in the Safety Population in the respective treatment group who have solicited data reported for the corresponding day. Severity is the maximum severity reported post dosing for each subject for each day.

Table 69: Number and Percentage of Subjects Experiencing Solicited Adverse Events of Mild Severity or Greater, Moderate Severity or Greater, or Severe Severity Over the Follow-up Period by Treatment Group - Safety Population

Symptom	Severity	Azithromycin (N=X)		Placebo (N=X)		Risk Difference (95% CI) ^b	P-Value ^c
		n (%)	95% CI ^a	n (%)	95% CI ^a		
Any Symptom	Mild or Greater	x (x)	(x, x)	x (x)	(x, x)	x.x (x.x, x.x)	x.xxx
	Moderate or Greater	x (x)	(x, x)	x (x)	(x, x)	x.x (x.x, x.x)	x.xxx
	Severe	x (x)	(x, x)	x (x)	(x, x)	x.x (x.x, x.x)	x.xxx
Abdominal Pain	Mild or Greater	x (x)	(x, x)	x (x)	(x, x)	x.x (x.x, x.x)	x.xxx
	Moderate or Greater	x (x)	(x, x)	x (x)	(x, x)	x.x (x.x, x.x)	x.xxx
	Severe	x (x)	(x, x)	x (x)	(x, x)	x.x (x.x, x.x)	x.xxx
Vomiting	Mild or Greater	x (x)	(x, x)	x (x)	(x, x)	x.x (x.x, x.x)	x.xxx
	Moderate or Greater	x (x)	(x, x)	x (x)	(x, x)	x.x (x.x, x.x)	x.xxx
	Severe	x (x)	(x, x)	x (x)	(x, x)	x.x (x.x, x.x)	x.xxx
Diarrhea	Mild or Greater	x (x)	(x, x)	x (x)	(x, x)	x.x (x.x, x.x)	x.xxx
	Moderate or Greater	x (x)	(x, x)	x (x)	(x, x)	x.x (x.x, x.x)	x.xxx
	Severe	x (x)	(x, x)	x (x)	(x, x)	x.x (x.x, x.x)	x.xxx
Allergic Reaction	Mild or Greater	x (x)	(x, x)	x (x)	(x, x)	x.x (x.x, x.x)	x.xxx
	Moderate or Greater	x (x)	(x, x)	x (x)	(x, x)	x.x (x.x, x.x)	x.xxx
	Severe	x (x)	(x, x)	x (x)	(x, x)	x.x (x.x, x.x)	x.xxx
Candidiasis	Mild or Greater	x (x)	(x, x)	x (x)	(x, x)	x.x (x.x, x.x)	x.xxx
	Moderate or Greater	x (x)	(x, x)	x (x)	(x, x)	x.x (x.x, x.x)	x.xxx
	Severe	x (x)	(x, x)	x (x)	(x, x)	x.x (x.x, x.x)	x.xxx

N = Number of subjects in the Safety population who have solicited data reported.

^a95% CI for proportions calculated using the Wilson method.

^b95% CI for the difference in proportions, placebo relative to azithromycin, calculated using the Miettinen–Nurminen method.

^cP-values from Fisher’s exact test.

